8.1.3. Recording Adverse Events

All AEs/SAEs will be entered into the electronic database.

Planned hospital admissions or surgical procedures for an illness or disease that existed before the subject was enrolled in the study are not to be considered AEs unless they occur at a time other than the planned date or the pre-existing illness or disease worsens after enrollment into the study.

Fractures identified during the study are not to be recorded as AEs unless the subject is hospitalized, the fracture is complicated, or the Investigator considers the fracture to be unrelated to the subject’s underlying osteoporosis. All fractures will be identified and evaluated as part of the disease assessment and will be documented in the case report form and by collection of source documents.

For both serious and non-serious adverse events, the Investigator must determine the intensity of the event and the relationship of the event to study drug administration. Intensity for each AE will be defined according to the following criteria:

Intensity	Definition
Mild	Awareness of sign or symptom, but easily tolerated.
Moderate	Discomfort enough to cause interference with normal daily activities.
Severe	Inability to perform normal daily activities.

If the intensity of an adverse event changes within a day, the maximum intensity should be recorded. If the intensity changes over a longer period of time, the changes should be recorded as separate events (having separate onset and stop dates for each intensity).

Relationship to blinded study drug administration will be determined by the Investigator according to the following criteria:

Relationship	Definition
None	No relationship between the event and the administration of study drug. The event is related to other etiologies, such as concomitant medications or subject's clinical state.
Unlikely	The current state of knowledge indicates that a relationship to study drug is unlikely or the temporal relationship is such that study drug would not have had any reasonable association with the observed event.
Possible	A reaction that follows a plausible temporal sequence from administration of the study drug and follows a known response pattern to the suspected study drug. The reaction might have been produced by the subject's clinical state or other modes of therapy administered to the subject.

Relationship	Definition
Probable	A reaction that follows a plausible temporal sequence from administration of the study drug and follows a known response pattern to the suspected study drug. The reaction cannot be reasonably explained by the known characteristics of the subject's clinical state or other modes of therapy administered to the subject.

For the purpose of safety analyses, all AEs that are classified with a relationship to study medication administration of possible or probable will be considered treatment-related events.

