8. ADVERSE EVENT AND SERIOUS ADVERSE EVENT DOCUMENTATION

8.1. Evaluation of Safety

Timely, accurate, and complete reporting and analysis of safety information from clinical studies are crucial for the protection of subjects and is mandated by Regulatory Agencies worldwide. All clinical studies sponsored by RADIUS will be conducted in accordance with Standard Operating Procedures (SOPs) that have been established to conform to regulatory requirements worldwide to ensure appropriate reporting of safety information.

All AEs are collected from the time of the informed consent until 30 days after last dose of investigational product. Where possible, a diagnosis rather than a list of symptoms should be recorded. All AEs should be captured on the appropriate AE pages in the eCRF and in source documents. The Investigator will assess all AEs and determine reporting requirements to the Sponsor as well as the IRB.

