8.1.1. Adverse Events

An AE is any untoward medical occurrence in a clinical investigation subject administered a pharmaceutical product and that does not necessarily have a causal relationship with this treatment. An AE can therefore be any unfavorable and unintended sign (including an abnormal laboratory finding), symptom, or disease temporally associated with the use of a medicinal (investigational) product, whether or not related to the medicinal (investigational) product (ICH, 1995).

AEs include:

Worsening (change in nature, severity, or frequency) of conditions present at the onset of the study

- Intercurrent illnesses
- Drug interactions
- Events related to or possibly related to concomitant medications
- Abnormal laboratory values (this includes significant shifts from Baseline within the range of normal that the Investigator considers to be clinically important)
- Clinically significant abnormalities in physical examination, vital signs, and weight

An abnormal laboratory value will not be assessed as an AE unless it requires a therapeutic intervention or is considered by the Investigator to be clinically significant.

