8.1.2. Serious Adverse Events

A serious adverse event (SAE) is any AE that results in any of the following:

- Death
- Life-threatening: The term “life-threatening” in the definition of “serious” refers to an event/reaction in which the subject was at risk of death at the time of the event/reaction; it does not refer to an event/reaction which hypothetically might have caused death if it were more severe
- Required inpatient hospitalization or prolongation of existing hospitalization
- A persistent or significant disability/incapacity (ie, substantial disruption of the ability to conduct normal life function)
- Congenital anomaly/birth defect

Important medical events that may not result in death, are life-threatening, or require hospitalization may be considered serious when, based upon appropriate medical judgment, they may jeopardize the subject and may require medical or surgical intervention to prevent one of the outcomes listed in this definition. Examples of such medical events include allergic bronchospasm requiring intensive treatment in an emergency room or at home, blood dyscrasias or convulsions that do not result in inpatient hospitalization, or the development of drug dependency or drug abuse.

All adverse events of osteosarcoma will be reported as SAEs. All reports of osteosarcoma, regardless of causality or expectedness, will be expedited to the FDA within 15 days of receipt. MedDRA preferred terms include osteosarcoma, osteosarcoma metastatic, osteosarcoma recurrent, extraskelatal osteosarcoma, extraskelatal osteosarcoma metastatic, extraskelatal osteosarcoma recurrent.

All SAEs must be followed until resolution (subject has returned to baseline status of health) or until stabilization (the Investigator does not expect any further improvement or worsening of the reported event).

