8.1.4. Serious Adverse Event (SAE) Reporting

Any SAEs that occur during the study from the time the subject signs the ICF until 30 days after the last dose of study medication must be reported within 24 hours of first awareness of the event to RADIUS Pharmacovigilance. These events will be followed until resolution or stabilization. The reference safety information for this study is included in the Investigator Brochure, which will be provided under separate cover to all Investigators.

Any SAEs that occur at any time after completion of the study, which the Investigator considers to be related to study drug, must be reported to the Sponsor or its designee.

The Investigator must submit the SAE to the IRB in accordance with 21 CFR parts 56 and 312 as well as with applicable local regulations. Documentation of these submissions must be retained in the site study file.

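### The fracture exemption in Protocol 8.1.3 does not carry over the seriousness criteria of 8.1.2, so 8.1.2, 8.1.3 and the 24-hour rule in 8.1.4 need to be reconciled

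*Protocol*

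**What the plan says.** **The exemption.** Protocol 8.1.3: "Fractures identified during the study are not to be recorded as AEs unless the subject is hospitalized, the fracture is complicated, or the Investigator" attributes the fracture to something other than the osteoporosis. The same paragraph says that every fracture is evaluated as disease assessment and documented in the case report form with source documents. The opening line of 8.1.3, by contrast, requires all AEs and SAEs to be entered in the database.

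**The SAE definition.** Protocol 8.1.2: "A serious adverse event (SAE) is any AE that results in any of the following". The list is death, threat to life, hospitalization, "A persistent or significant disability/incapacity" and congenital anomaly. A further paragraph adds: "Important medical events that may not result in death, are life-threatening, or require hospitalization may be considered serious", on medical judgment.

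**The reporting duty.** Protocol 8.1.4 says that any SAE from consent to 30 days after the last dose "must be reported within 24 hours of first awareness of the event to RADIUS Pharmacovigilance". It makes no exception for fractures.

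**The general rules.** Protocol 8.1.1: "An AE is any untoward medical occurrence in a clinical investigation subject administered a pharmaceutical product". That definition does not exclude fractures. Protocol 8.1: "All AEs should be captured on the appropriate AE pages in the eCRF and in source documents".

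**The outputs.** SAP 4.7.1 builds the severe, serious and drug-related tables from TEAEs. SAP 4.7.6 gives the number and percentage of subjects with a post-baseline clinical fracture, and its location.

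**The concern.** Under 8.1.2 an SAE is an AE first. A rule that keeps a class of events off the AE record should therefore let back in everything that 8.1.2 would call serious. The exemption in 8.1.3 names one seriousness criterion, hospitalization, and adds an undefined word, *complicated*.

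Consider an osteoporotic fracture that is treated without admission and judged uncomplicated, but that substantially disrupts normal life or that the investigator regards as medically important. Section 8.1.3 tells the site not to record it as an AE, while 8.1.2 and 8.1.4 tell the site to report it within 24 hours. A site that follows 8.1.3 to the letter would leave the event outside expedited reporting, the intensity and relationship assessments, and the serious-event table.

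**Working it through.** No arithmetic applies, because the point rests on wording. The check has three steps.

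**Step 1. Match each criterion in 8.1.2 to the exceptions in 8.1.3, for a fracture attributed to osteoporosis.**

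| Seriousness criterion (8.1.2) | Named in the 8.1.3 exception? | Route back to the AE record |
|---|---|---|
| Hospitalization | Yes | Explicit |
| Death | No | Only as *complicated*, which a site would probably apply |
| Threat to life | No | Only as *complicated*, which a site would probably apply |
| Disability or incapacity | No | Only on a broad reading of *complicated* |
| Important medical event | No | Only on a broad reading of *complicated* |
| Congenital anomaly | No | Not relevant to a fracture in this population |

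Only hospitalization is in both lists. The realistic gap is the disability row and the important-medical-event row.

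**Step 2. Test both readings of the exemption.**

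- *The fracture remains an AE and is merely not recorded as one.* Sections 8.1.2 and 8.1.4 then apply and a serious fracture is reportable. But the instruction not to record it contradicts the opening line of 8.1.3 and the rule in 8.1 that all AEs go on the AE pages.
- *The fracture is not an AE.* It then cannot be an SAE under 8.1.2, and the 24-hour duty never starts.

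The first reading leaves two instructions that a site cannot both follow. The second leaves a gap in reporting. Either way the text needs repair.

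**Step 3. Trace what an exempt fracture loses.**

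- *Timing.* The 24-hour duty runs from first awareness of an SAE. No deadline is stated for fracture documentation. Under Protocol 7.2.7 the subject is reminded to bring films and reports to the next visit. Section 7.2 sets a month at 30 days, so the Month 1 and Month 3 visits are nominally 2 × 30 = 60 days apart.
- *Assessment.* Section 8.1.3 requires intensity and relationship for adverse events. No such requirement is stated for a fracture held only as disease assessment.
- *Tables.* The fracture is absent from the serious, severe and drug-related TEAE tables of SAP 4.7.1. It is counted in SAP 4.7.6, which shows no seriousness, intensity or relationship. Under SAP 3.2, summaries include sub-study data only up to Month 4, with later data in listings.

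**The case against.** The case on the other side has real force.

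- **Wording.** Section 8.1.3 says that fractures are not *recorded* as AEs, whereas planned admissions, in the paragraph above, are not to be *considered* AEs. A serious fracture can therefore still be an AE under 8.1.1 and reportable under 8.1.4. This stands. A reader might infer that such fractures can never reach the SAE pathway, and the documents do not support that.
- ***Complicated* may cover much of the gap.** A fatal or life-threatening fracture is hard to call uncomplicated. The exemption also covers the fracture itself, and nothing in it exempts the medical consequences of a fracture. This stands, and it narrows the gap to the disabling or medically important outpatient fracture. It does not close it, because the word is undefined.
- **Other safeguards exist.** Protocol 5.3.1 provides for consultation with the Medical Monitor and an offer to discontinue after an incident fragility fracture. It also requires an additional consent form if a subject with a clinical fragility fracture stays in the study. New fractures are assessed at every visit from Visit 2, all are documented, and SAP 4.7.6 tabulates post-baseline clinical fractures. So it would be wrong to infer that they disappear from the study or from its safety output. But none of these routes sets a 24-hour limit or requires a seriousness or relationship judgment.
- **The convention is deliberate.** Handling fractures as disease assessment avoids recording routine osteoporotic fractures twice. That aim is reasonable, and it can be kept while the seriousness criteria are restored.

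**Conclusion.** The point holds as an inconsistency. Section 8.1.3 does not ensure that an osteoporotic fracture meeting a seriousness criterion other than hospitalization is recorded and reported as an SAE. It conflicts with 8.1.2, with 8.1.4 and with its own opening line. The conclusion assumes that a site may apply 8.1.3 literally and may read *complicated* narrowly. The text permits both but compels neither.

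The size cannot be estimated. The documents give no expected fracture rate, and few qualifying events are likely in about 25 women treated for 3 months (6 months in the sub-study). One might be tempted to say that a single missed event moves the serious-event rate by 1/25 = 4%. That is true of any single event in 25 subjects and says nothing about how often this one would occur.

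Safety analyses are descriptive. The primary endpoint, the power and the error rate are untouched. The correction is worth making because it concerns expedited safety reporting and costs very little.

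**What to change.** Reconcile 8.1.2, 8.1.3 and 8.1.4 with one clause. In the 8.1.3 exemption, replace the hospitalization exception with: *the fracture meets any seriousness criterion in Section 8.1.2 (in which case it is recorded and reported as an SAE under Section 8.1.4)*. Hospitalization is itself a criterion in 8.1.2, so that exception is not lost. Keep the other two exceptions (complicated; not attributed to osteoporosis).

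A broader rewording that adds fractures related to a study procedure is not needed for this defect. A fracture caused by a procedure would ordinarily fall under the existing exception for fractures not attributed to osteoporosis.

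Leave the fracture documentation and SAP 4.7.6 unchanged. Fractures that return to the AE record will reach the SAP 4.7.1 tables through the existing TEAE definition. The cost is one clause in the protocol, the matching line in any eCRF completion guidance, and a few additional AE/SAE forms.

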8.1.4. Serious Adverse Event (SAE) Reporting

Any SAEs that occur during the study from the time the subject signs the ICF until 30 days after the last dose of study medication must be reported within 24 hours of first awareness of the event to RADIUS Pharmacovigilance. These events will be followed until resolution or stabilization. The reference safety information for this study is included in the Investigator Brochure, which will be provided under separate cover to all Investigators.

Any SAEs that occur at any time after completion of the study, which the Investigator considers to be related to study drug, must be reported to the Sponsor or its designee.

The Investigator must submit the SAE to the IRB in accordance with 21 CFR parts 56 and 312 as well as with applicable local regulations. Documentation of these submissions must be retained in the site study file.

8.1.5. Follow-up of Adverse Events

All AEs will be followed with appropriate medical management until resolved or stabilized.

8.1.6. Abuse, Misuse, Overdose, or Medication Error

Abuse, misuse, overdose or medication error (as defined below) must be reported to the Sponsor whether or not they result in an AE/SAE.

- Abuse – Persistent or sporadic intentional intake of investigational medicinal product at a dose higher than prescribed per protocol (but below the dose defined for overdose) or when used for non-medical purpose (eg, altering one's state of consciousness).
- Misuse – Intentional or unintentional use of investigational medicinal product other than as directed or indicated at any dose, which is at or below the dose defined for overdose Note: this includes a situation where the test article is not used as directed at the dose prescribed by the protocol.

- Overdose – Intentional or unintentional injection of a dose of abaloparatide at least 2 times higher than the protocol specified dose and is associated with clinical symptoms.
- Medication Error – A mistake made in prescribing, dispensing, administration and/or use of the investigational medicinal product.

8.1.7. Regulatory Agency, Institutional Review Board, Ethics Committee and Site Reporting

The Sponsor and/or the clinical contract research organization (CRO) are responsible for notifying the relevant regulatory authorities/US central Institutional Review Boards (IRBs)/EU central ethics committees (ECs) of related, unexpected SAEs.

The Investigator is responsible for notifying the Sponsor, CRO, and local IRB, local EC, or the relevant local regulatory authority of all SAEs that occur at his or her site as required.

If a death occurs during the study or within 30 days after Month 3/Early Termination visit (Visit 5), and it is determined to be related either to a study procedure or study drug, the Investigator or his/her designee must notify the Sponsor and will communicate that information to the IRB within one business day of knowledge of the event. The contact may be by phone or e-mail.

8.2. Study Completion and Post-Study Treatment

The Investigator must provide follow-up medical care for all subjects who are prematurely withdrawn from the study due to an adverse event or must refer them for appropriate ongoing care.

8.3. Lost to Follow-up

For subjects whose status is unclear because they fail to appear for study visits without stating an intention to discontinue or withdraw, the Investigator should show "due diligence" by documenting in the source documents steps taken to contact the subject, eg, dates of telephone calls, registered letters, etc. A subject should not be formally considered lost to follow-up until his/her scheduled end of study visit would have occurred.

9. STATISTICAL CONSIDERATIONS

9.1. Statistical Analysis Plan

A comprehensive Statistical Analysis Plan (SAP) will be completed and approved prior to database lock. All statistical tests will be two-sided with a significance level of 5%, unless otherwise specified.

9.2. Statistical Hypothesis

9.3. Analysis Datasets

9.3.1. Population for Analysis

The primary population for all efficacy analyses will be the Bone-Biopsy Population, which is defined as all enrolled subjects who received a biopsy. The primary population for all safety analyses will be the Safety Population, which will be defined as all enrolled subjects who received at least one dose of abaloparatide.

9.4. Description of Statistical Methods

9.4.1. General Approach

Baseline is defined as the last value obtained prior to the first dose of study medication.

For categorical data, summary tabulations of the number and percentage of subjects within each category of the parameter will be presented. For continuous data, the number of subjects, mean, median, standard deviation (SD), minimum, interquartile range (Q1 and Q3), and maximum will be presented.

9.4.2. Analysis of the Primary Efficacy Endpoint(s)

The primary endpoint of this study is the change from baseline to 3 months in mineralizing surface (MS/BS) in the cancellous bone envelope. Paired t-tests will be used to compare the differences in dynamic indices between the two time-points derived from the two sets of double labels using the Bone-Biopsy Population. If the normality assumption of the efficacy data is not satisfied at the 0.01 significance level and if visual inspection of the data deems it necessary, an appropriate nonparametric test, such as the Wilcoxon signed-rank test, will be used to assess changes from baseline. No adjustments for multiplicity will be made. A p-value < 0.05 will be considered statistically significant.

9.4.3. Analysis of Secondary Endpoint(s)

Secondary efficacy endpoints of tissue-based indices of bone formation and bone resorption will be analyzed in the same manner as the analysis of the primary efficacy endpoint using the Bone Biopsy Population.

The change and percent change from baseline in bone turnover makers (s-PINP and s-CTX) will be summarized descriptively at each visit (1 and 3 months) using the Bone-Biopsy and the Safety Populations.

Linear regression analyses will be used to assess the relationships between efficacy endpoints of tissue-based indices of bone formation and bone resorption and changes in bone turnover markers at each visit, including changes in MS/BS and BFR/BS in each envelope to changes in s-PINP, changes in intracortical MS/BS and BFR/BS to changes in s-CTX, MS/BS and BFR/BS in each envelope at Month 3 to s-PINP at Months 1 and 3, intracortical MS and BFR/BS at Month 3 to s-CTX at Month 3, and ES/BS in each envelope and cortical porosity at Month 3 to s-CTX at Month 3. The analyses include scatter plots, Pearson's correlation coefficient, and slopes of simple regression models using the Bone-Biopsy Population.

9.4.4. Safety Analyses

Unless otherwise specified, safety analyses will be conducted using the Safety Population and will be descriptive in nature.

Study drug exposure and study drug compliance will be calculated. The duration of study drug exposure, total dose received, and percent compliance will be summarized.

All AEs will be coded using MedDRA. The number and percent of subjects who experienced treatment-emergent AEs (TEAEs) will be summarized by MedDRA system organ class (SOC), and preferred term (PT). Summaries will also be provided for severe TEAEs, serious TEAEs (SAEs), TEAEs leading to study drug withdrawal, drug-related TEAEs (with probable or possible relationship to study drug), and TEAEs by maximum severity (mild, moderate, severe).

The number and percent of subjects who report TEAEs associated with hypercalcemia and hypercalciuria will be summarized.

All AEs collected prior to the first dose of study drug will be summarized separately.

Descriptive statistics for clinical laboratory data (including serum calcium and albumin), vital signs (including blood pressure), ECGs, and Investigator assessment of local tolerance will be provided by visit. For laboratory data, vital signs and ECGs, absolute results and changes from baseline will be presented. In addition, laboratory test results will be classified as above normal limit, within normal limit, or below normal limit. Laboratory shift frequencies will be tabulated between the Screening visit and relevant post-baseline visit(s).

Concomitant medications will be coded using the WHO Drug Dictionary and summarized by number and percentage of subjects using each class and preferred drug term.

